7.1.2 Temporary discontinuation

Temporary intervention discontinuation may be considered by the Investigator because of suspected AEs or disruption of the clinical trial due to a regional or national emergency declared by a governmental agency. For a regional or national emergency declared by a governmental agency, contingency measures are included in Appendix 9 ([Section 10.9](#)). For all temporary intervention discontinuations, duration should be recorded by the Investigator in the appropriate pages of the e-CRF.

In addition, the following conditions will be causes for temporary discontinuation of study intervention:

- Infections or infestations that do not respond to medical treatment.
- Treatment with a live (attenuated) vaccine.
- Treatment with immunomodulating biologics (including experimental treatments).
- Treatment with systemic corticosteroids (except systemic corticosteroids used to treat an asthma exacerbation) or systemic immunosuppressive drugs.
- Any laboratory abnormality that meets temporary treatment discontinuation criteria as per Appendix 5 ([Section 10.5](#)).

7.1.2.1 Rechallenge

Reinitiation of intervention with the IMP will be done under close and appropriate clinical/and or laboratory monitoring once the Investigator will have considered according to his/her best medical judgment that the responsibility of the IMP in the occurrence of the concerned event was unlikely and if the selection criteria for the study are still met (refer to [Section 5.1](#) and [Section 5.2](#)).

For a regional or national emergency declared by a governmental agency, contingency measures are included in Appendix 9 ([Section 10.9](#)).

7.2 PARTICIPANT DISCONTINUATION/WITHDRAWAL FROM THE STUDY

- A participant may withdraw from the study at any time at his/her own request or may be withdrawn at any time at the discretion of the Investigator for safety, behavioral, compliance, or administrative reasons. This is expected to be uncommon.
- Participants who prematurely discontinue the study, should attend an Early Study Discontinuation (ESD) visit at the earliest convenience with all the procedures planned for the End of Treatment Visit (Visit 5) except IMP, as shown in the SoA ([Section 1.3](#)). See SoA for data to be collected at the time of study discontinuation and follow-up and for any further evaluations that need to be completed. If the Investigator considers that the time from the last HRCT scan exposure is not acceptable, the investigation will not be done.
- The participant will be permanently discontinued both from the study intervention and from the study at that time.
- If the participant withdraws consent for disclosure of future information, the Sponsor may retain and continue to use any data collected before such a withdrawal of consent.
- If a participant withdraws from the study, he/she may request destruction of any samples taken and not tested, and the Investigator must document this in the site study records.

If participants no longer wish to take the IMP, they will be encouraged to remain in the study.

The investigators should discuss with them key visits to attend. The value of all their study data collected during their continued involvement will be emphasized as important to the public health value of the study.

Participants who withdraw from the study intervention should be explicitly asked about the contribution of possible AEs to their decision, and any adverse event (AE) information elicited must be documented.

All study withdrawals should be recorded by the Investigator in the appropriate screens of the e-CRF and in the participant's medical records. In the medical record, at least the date of the withdrawal and the reason should be documented.

In addition, a participant may withdraw his/her consent to stop participating in the study. Withdrawal of consent for intervention should be distinguished from withdrawal of consent for follow-up visits and from withdrawal of consent for non-participant contact follow-up, eg, medical record checks. The site should document any case of withdrawal of consent.

Participants who have withdrawn from the study cannot be rerandomized/reallocated (treated) in the study. Their inclusion and intervention numbers must not be reused.

7.3 LOST TO FOLLOW UP

A participant will be considered lost to follow-up if he or she repeatedly fails to return for scheduled visits and is unable to be contacted by the study site.

The following actions must be taken if a participant fails to return to the clinic for a required study visit:

- The site must attempt to contact the participant and reschedule the missed visit as soon as possible and counsel the participant on the importance of maintaining the assigned visit schedule and ascertain whether or not the participant wishes to and/or should continue in the study.
- Before a participant is deemed lost to follow-up, the Investigator or designee must make every effort to regain contact with the participant (where possible, 3 telephone calls and, if necessary, a certified letter to the participant's last known mailing address or local equivalent methods). These contact attempts should be documented in the participant's medical record.
- Should the participant continue to be unreachable, he/she will be considered to have withdrawn from the study.

Discontinuation of specific sites or of the study as a whole are handled as part of Appendix 1 ([Section 10.1.9](#)).

8 STUDY ASSESSMENTS AND PROCEDURES

- Study procedures and their timing are summarized in the SoA ([Section 1.3](#)). Protocol waivers or exemptions are not allowed.
- Adherence to the study design requirements, including those specified in the SoA, is essential and required for study conduct.
- All screening evaluations must be completed and reviewed to confirm that potential participants meet all eligibility criteria. The Investigator will maintain a screening log to record details of all participants screened and to confirm eligibility or record reasons for screening failure, as applicable.
- Procedures conducted as part of the participant's routine clinical management (eg, blood eosinophil count, reversibility test) and obtained before signing of the ICF may be utilized for screening purposes provided the procedures met the protocol-specified criteria and were performed within the time frame defined in the SoA.
- The lab tests will be done by the local laboratories, the maximum amount of blood collected from each participant over the duration of the study will be according to the routine clinical practice in each country and site. As the blood analysis will be performed by the local laboratories, any leftover blood sample will not be used for any other research purposes related to the study (re-analyses) or for future exploratory use (secondary use). Repeat or unscheduled samples may be taken for safety reasons or for technical issues with the samples.
- For a regional or national emergency declared by a governmental agency, contingency measures are included in Appendix 9 ([Section 10.9](#)).

8.1 EFFICACY ASSESSMENTS

Disease-specific efficacy measures

Spirometry

A spirometer that meets the American Thoracic Society(ATS)/European Respiratory Society (ERS) recommendations will be used. Spirometry should be performed in accordance with these recommendations ([36](#)).

For pre-bronchodilator measured parameters, including FEV₁ and FVC spirometry will be performed after withholding the standard of care asthma treatment as follows:

Table 4 - Wash out period of asthma controllers and rescue medication before HRCT scan and lung function assessments

Oral Xanthine derivatives	72 hours
Long-acting beta agonists (LABA) (eg, salmeterol)	24 hours
Long-acting muscarinic antagonist(LAMA) (eg, Tiotropium)	48 hours
Inhaled ICS	12 hours
Inhaled ICS/LABA	24 hours
Inhaled Ultralong ICS/LABA combinations	48 hours

Inhaled and/or nebulized SABAs (eg, salbutamol)	6 hours
Inhaled and/or nebulized SAMAs (eg, ipratropium)	8 hours
SABA/SAMA combination	8 hours
Inhaled and/or nebulized corticosteroid (ICS)	12 hours
Long-acting beta agonists (LABA)	24 hours
Long-acting muscarinic antagonist (LAMA)	48 hours
Inhaled ICS/LABA	24 hours
Systemic corticosteroids (oral, IM, IV)	4 weeks

This will be verified before performing the measurements.

In case of asthma exacerbations treated with systemic corticosteroids, the visits can be postponed up to 1 week to ensure the wash-out period before performing HRCT scan, FeNO, FOT and spirometry. In case this is not possible (eg, a participant experiences an exacerbation shortly before the scheduled visit), the procedures can be performed as planned, but it should be recorded that the participant had recently taken systemic corticosteroids.

For post-bronchodilator FEV₁, the measurement should follow the steps as that at screening test for reversibility validation.

At all visits, spirometry should be performed before IMP administration, in the morning, if possible. The same spirometer and standard spirometric techniques, including calibration, will be used to perform spirometry at all visits and, whenever possible, the same person should perform the measurements; afternoon/evening is allowable in the exceptional circumstance when morning spirometry cannot be performed; spirometry should be done at approximately the same time at each visit throughout the study.

Pulmonary function tests will be measured in the sitting position; however, if necessary to undertake the testing with the subject standing or in another position, this should be noted on the spirometry report. For any subject, the position should be consistent throughout the study.

Three measurements fulfilling the ATS acceptability and repeatability criteria should be obtained at every visit. The acceptability criteria must be applied before the repeatability criteria. Unacceptable maneuvers must be discarded before applying the repeatability criteria. At least 2 acceptable curves must be obtained.

The largest FEV₁ and largest FVC should be recorded after the data are examined from all of the acceptable curves, even if they do not come from the same curve.

The spirometer must be calibrated following the principles of the ATS/ERS guidelines every day that a study subject is seen, and spirometry is carried out. The calibration records should be kept in a reviewable log. It is preferred that the calibration equipment (ie, 3-liter syringe) that is used to calibrate the spirometer be subjected to a validated calibration according to the manufacturer's specifications. A participant who is unable to complete a successful spirometry effort as defined by ATS criteria or evaluated by the investigator or did not meet the eligibility criterion for pre-BD FEV₁ at V1 can be retested one additional time during the screening period of the study. The

spirometry will be centrally read. The locally read values of FEV₁ will be considered for the participant qualification into the study at V1 and V2. For the statistical analysis we will use centrally read values. Further details on the procedure will be provided in a separate instructions manual.

Reversibility

A reversibility test will be administered following pulmonary function testing after asthma medications have been withheld for the appropriate intervals. Subjects will receive 2 to up to 4 puffs of albuterol/salbutamol from a primed metered dose inhaler (MDI). Alternatively, and only if it is consistent with usual office practice (to be documented), reversibility may be performed using inhalation of nebulized albuterol/salbutamol. Spirometry may be repeated several times within 30 minutes after administration of bronchodilator. Reversibility, which is defined as an increase in absolute FEV₁ of 12% over the baseline value, with an absolute increase of at least 200 mL, must be demonstrated within 30 minutes of bronchodilator administration. If the participant does not meet the eligibility criterion for reversibility at V1, up to 3 attempts may be performed during the screening period. This is only required if a reversibility test meeting eligibility criterion was not performed within 6 months prior to V1.

Asthma Control Questionnaire 7-question version

The ACQ-7 is comprised of 7 items: the first 5 items assess the most common asthma symptoms: 1. frequency in past week awoken by asthma during the night; 2. severity of asthma symptoms in the morning; 3. limitation of daily activities due to asthma; 4. shortness of breath due to asthma; and 5. wheeze; plus question 6. short-acting bronchodilator use; and 7. FEV₁ (% predicted). Participants are asked to recall how their asthma has been during the previous week and to respond to the symptom questions on a 7-point scale (0=no impairment, 6=maximum impairment).

Clinic staff score for FEV₁% is predicted on a 7-point scale. The details are given in [Table 5](#).

Table 5 - Clinic staff score for FEV₁%

FEV₁% predicted	Score
>95% predicted	0
95%-90%	1
89%-80%	2
79%-70%	3
69%-60%	4
59%-50%	5
<50%	6

Abbreviation: FEV₁ = forced expiratory volume in 1 second

A global score is calculated: the questions are equally weighted and the ACQ-7 score is the mean of the 7 questions and, therefore, between 0 (totally controlled) and 6 (severely uncontrolled). Higher score indicates lower asthma control. Participants with a score below 1.0 reflect adequately controlled asthma and participants with scores above 1.0 reflect inadequately

controlled asthma. On the 7-point scale of the ACQ-7, a change or difference in score of 0.5 is the smallest change that can be considered clinically important, corresponding to the Minimal Clinically Important Difference (MCID) defined by the developer.

The participants will complete the ACQ-7 on paper.

Asthma Control Questionnaire items 1 to 6 should be completed by the participant, independently from their physician, the study nurse or any other medical personnel and without any help from friends or relatives. The questionnaire should be completed by the participants before the consultation and clinical tests, including spirometry, in a quiet place.

The ACQ-5 (Mean of the responses to the first 5 questions) and ACQ-6 (Mean of the responses to the first 6 questions) will be derived from ACQ-7. For the ACQ-7 scores will be considered the local values of FEV₁. For the statistical analysis we will use the centrally read values.

Asthma Quality of Life Questionnaire with Standardized Activities (Self-Administered)

Asthma Quality of Life Questionnaire with Standardized Activities (AQLQ[S]) was designed as a self-administered patient-reported outcome to measure the functional impairments that are most troublesome to adolescents ≥ 12 years of age and adults as a result of their asthma. The instrument is comprised of 32 items, each rated on a 7-point Likert scales from 1 to 7. The AQLQ(S) has 4 domains. The domains and the number of items in each domain are as follows:

- Symptoms (12 items).
- Activity limitation (11 items).
- Emotional function (5 items).
- Environmental Stimuli (4 items).

Individual items are equally weighted. The overall score is the mean of response to each of the 32 questions (ranging from 1 to 7). Higher scores indicate better quality of life. The instrument has been used in many clinical trials, and it has been shown to be reliable, valid (participant interviews), and sensitive to change. The MCID for AQLQ(S) is 0.5 ([37](#)).

The participants will complete the AQLQ(S) on paper.

Asthma Quality of Life Questionnaire with Standardized Activities (AQLQ[S]) should be completed by the participant, independently from their physician, the study nurse or any other medical personnel and without any help from friends or relatives. The questionnaire should be completed by the participants before the consultation and clinical tests, including spirometry, in a quiet place.

Forced Oscillometry

Asthma is an inflammatory airway disease affecting the entire bronchial tree, including the small airways, defined as those with an internal diameter of 2 mm or less. Multiple lines of evidence suggest that, within subjects with asthma, the small airways are dysfunctional ([38](#)), inflamed ([39](#)), and damaged ([40](#)), therefore playing an important role in asthma. Forced oscillation technique (FOT) R5 - R20 is a direct measure of anatomical narrowing in the small airways ([41](#)). The FOT

determines breathing mechanics by superimposing small external pressure signals on the spontaneous breathing of the subject. It is indicated as a diagnostic method to obtain reliable differentiated tidal breathing analysis. As FOT is performed without closure of a valve connected to the mouthpiece, and without maximal or forced respiratory maneuvers, it is unlikely that FOT itself will alter airways smooth muscle tone.

Forced oscillation technique utilizes the external applied pressure signals and their resultant flows to determine lung mechanical parameters. These pressure-flow relationships are largely distinct from the natural pattern of individual respiratory flows, so that measured FOT results are, for the most part, independent of the underlying respiratory pattern. Therefore, oscillometry minimizes demands on the participant and requires only passive cooperation of the subject: maintenance of an airtight seal of the lips around a mouthpiece and breathing normally through the measuring system with a nose-clip occluding the nares. FOT should be conducted prior to spirometry. The assessment will be done by central reading. Further details on the procedure will be provided in a separate instruction manual.

Fractional Exhaled Nitric Oxide

Fractional exhaled nitric oxide will be analyzed using a NIOX instrument using a flow rate of 50 mL/s and reported in ppb. This assessment should be conducted prior to spirometry and the participant should refrain from eating and drinking for at least 1 hour prior to the procedure. The test will be performed after a wash out period of bronchodilators according to their action duration as detailed in [Table 4 \(Section 8.1\)](#). Retesting of FeNO can be done one additional time during screening if the eligibility criterion for FeNO was not met at V1. FeNO will be re-checked at randomization visit (V2) for eligibility. Further details on the procedure for measuring exhaled nitric oxide with NIOX will be provided in a separate instruction manual. FeNO assessment will be performed by local reading. The recommendation is to perform the investigations in the following order: FeNO, FOT, spirometry.

Functional Respiratory Imaging

Functional Respiratory Imaging is a non-invasive measurement of the participant specific respiratory system. A set of distinct imaging parameters analyzes exposure, structure and function of the lungs and airways in asthma.

The process starts with the acquisition of low dose, pre-bronchodilator HRCT scans of the participant.

The measurements are performed on the segmented 3-dimensional geometries from these scans. Computational fluid dynamics (CFD) is used to quantify airflow and exposure.

Airway Volume ([s]iVaw)

(s)iVaw is the change of volume of the airways (in mL), taking into account the lung volume changes (in L) as well.

[figure not shown]
With anti-inflammatory compounds, often the lung volumes reduce (they become less inflamed), while the airway volumes increase, since lower volume increase airway resistance showing a better picture of the true dynamics of the airways versus the lung volumes.

The anti-inflammatory effect of dupilumab can be described in terms of changes in airway caliber such as airway volumes ([s]iVaw).

Airway caliber changes are more sensitive compared to FEV₁ hence can provide additional insights into potential remodeling and additional improvements not described by FEV₁ (eg, between Weeks 4 and 24).

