15.3. Missing efficacy data

Asthma Control Questionnaire (ACQ-7, ACQ-6 and ACQ-5)

- Based on the manual of ACQ (2), any more than one missing value is not acceptable. If more than one of the questions have missing value, the global score is invalid and will be considered as missing. If only one question has missing score, it will be interpolated (pro-rated) using the completed questionnaires from the previous visit. For instance, answer to question 5 is missing at Visit 4, and all questions are completed at Visit 3. Then the question 5 score at Visit 4 is interpolated as: (sum of score at Visit 4/sum of scores excluding question 5 at Visit 3) × score of question 5 at Visit 3. If the questionnaire from the previous visit is not complete either, the missing value will be imputed as the average of the completed questions within the current visit.

Asthma Quality of Life Questionnaire (AQLQ)

- To have a valid overall score, it is not acceptable to have more than three missing responses or more than one missing response per domain. For responses with more than acceptable amount of missing value(s), the overall score will be considered as missing. For responses with amount of missing value(s) within accept range, the missing score will be interpolated using the previous completions of the questionnaire following the similar algorithm used for ACQ.

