15.8. Participant-Reported Outcomes (PROs)

Asthma Control Questionnaire (ACQ-7, ACQ-6 and ACQ-5)

Asthma Control Questionnaire-7 (ACQ-7) collects participants assessment of their asthma during the previous week based on 6 questions on a 7-point scale (0 = no impairment to 6 = maximum impairment) and a scoring of the FEV₁% predicted by clinic staff, also on a 7-point scale.

The ACQ was designed to measure both the adequacy of asthma control and change in asthma control which occurs either spontaneously or as a result of study intervention.

The ACQ-7 has 7 questions with the first 5 items assessing the most common asthma symptoms (corresponding to ACQ-5),

The first 5 items assess the most common asthma symptoms:

1. frequency in past week awoken by asthma during the night
2. severity of asthma symptoms in the morning
3. limitation of daily activities due to asthma
4. shortness of breath due to asthma
5. wheeze
6. short-acting bronchodilator use
7. FEV₁ % predicted

The first 6 items will be used directly according to the result recorded on the 7-point scale (0 = no impairment to 6 = maximum impairment).

For Item 7, the Percent predicted FEV₁ value will be used and converted into the same 7-point scale, according to the following table:

FEV ₁ % predicted	Score
>95% predicted	0
95-90%	1
89-80%	2
79-70%	3
69-60%	4
59-50%	5
<50% predicted	6

A global score is calculated: the questions are equally weighted and the ACQ-7 score is the mean of the 7 questions and, therefore, between 0 (totally controlled) and 6 (severely uncontrolled). Higher score indicates lower asthma control. Participants with a score below 1.0 reflect adequately controlled asthma and participants with scores above 1.0 reflect inadequately controlled asthma. On the 7-point scale of the ACQ-7, a change or difference in score of 0.5 is the smallest change that can be considered clinically important, corresponding to the Minimal Clinically Important Difference (MCID) defined by the developer.

The participants will complete the ACQ-7 on paper. Asthma Control Questionnaire Items 1 to 6 should be completed by the participant, independently from their physician, the study nurse or any other medical personnel and without any help from friends or relatives. The questionnaire

should be completed by the participants before the consultation and clinical tests, including spirometry, in a quiet place.

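### The SAP's ratio rule for one missing ACQ item has no cap, no zero-denominator case and no exception for the FEV1 item, so it can return impossible or undefined item scores.

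*Protocol*

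**What the plan says.** Protocol 8.1 scores the symptom questions "on a 7-point scale (0=no impairment, 6=maximum impairment" and puts FEV1 % predicted on a seven-step score through Table 5. It concludes that "the ACQ-7 score is the mean of the 7 questions and, therefore, between 0 (totally controlled) and 6 (severely uncontrolled". SAP 15.8 gives the same range and adds that "For Item 7, the Percent predicted FEV₁ value will be used and converted into the same 7-point scale". Both documents treat a 0.5 change as the threshold of clinical importance: "a change or difference in score of 0.5 is the smallest change that can be considered clinically important".

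The missing-item rule is in SAP 15.3, under the heading "Asthma Control Questionnaire (ACQ-7, ACQ-6 and ACQ-5". With two or more items missing, the score is missing. Otherwise, "If only one question has missing score, it will be interpolated (pro-rated) using the completed questionnaires from the previous visit". The worked example fills question 5 at Visit 4 with "sum of score at Visit 4/sum of scores excluding question 5 at Visit 3) × score of question 5 at Visit 3". There is one fallback: if the previous questionnaire is also incomplete, the mean of the items completed at the current visit is used. For AQLQ(S), missing responses within the permitted number are "interpolated using the previous completions of the questionnaire following the similar algorithm used for ACQ".

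**The concern.** A ratio of two sums has no natural upper limit, while an item does. SAP 15.3 does not say what to do in three situations:

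- the filled value falls outside the item's scale;
- the previous-visit sum in the denominator is zero;
- the missing item is item 7, which is a spirometry band and not a patient's answer.

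Change in ACQ-7 at Week 24 is a listed secondary endpoint. A programmer following the text literally would produce impossible item values, some hidden inside plausible totals. A programmer who notices must improvise a rule at analysis. For item 7, a change in symptoms and reliever use would be recorded as a change in lung function.

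**Working it through.** **Inputs.** Items run 0 to 6 and ACQ-7 is the mean of seven (Protocol 8.1, SAP 15.8). The ratio rule is from SAP 15.3. Entry requires ACQ-5 of at least 1.5 and pre-bronchodilator FEV1 of at most 80% predicted (Protocol 5.1, I 03 and I 04).

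**Stated range, reproduced.** Minimum 0/7 = 0; maximum 7 × 6/7 = 6.

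**The rule.** Filled item x = (S_now / S_prev) × p. Here S_now and S_prev are the sums of the other items at the current and previous visits, and p is the previous score of the missing item. Then ACQ-7 = (S_now + x)/7.

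**1. Off-scale items.**
- Item 7 missing, p = 5, items 1 to 6 rising from 3 to 12: x = 12/3 × 5 = 20. ACQ-7 = (12 + 20)/7 = 4.57. The largest value possible with a valid item 7 is (12 + 6)/7 = 2.57. The excess is 2.0, four times the 0.5 threshold, yet the total still lies inside 0 to 6.
- Symptom item missing, p = 2, other items rising from 3 to 15: x = 15/3 × 2 = 10. ACQ-7 = 25/7 = 3.57, against at most (15 + 6)/7 = 3.00.
- Arithmetic worst case: x = 36/1 × 6 = 216, ACQ-7 = (36 + 216)/7 = 36.

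If every item pattern is taken as equally likely (an assumption for scale, not a forecast), the filled item exceeds 6 in about 14% of ACQ-7 patterns and the total exceeds 6 in about 0.3%. The usual failure is therefore an invalid item inside a valid-looking total.

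**2. Zero denominator.** If the other items were all 0 at the previous visit, x is S_now/0 or 0/0. The stated fallback does not apply, because the previous questionnaire was complete. From an eligible baseline this cannot occur. ACQ-5 of at least 1.5 means items 1 to 5 sum to at least 7.5, so 8 in whole numbers; dropping one item of at most 6 leaves at least 2. It can occur when the previous visit is post-baseline. SAP 8.2.4 and Table 15-2 analyse ACQ at Weeks 4 and 24, while the example in SAP 15.3 uses Visits 3 and 4. On either reading, the visit before Week 24 is post-baseline.

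**3. Item 7.** Items 1 to 6 fall from 12 to 0, the previous FEV1 score was 4 (60-69% predicted) and FEV1 is now missing: x = 0/12 × 4 = 0, the band above 95% predicted, with no spirometry. ACQ-7 becomes 0, against 4/7 = 0.57 if the band had not changed.

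**AQLQ(S).** Items run 1 to 7, so the denominator is never zero, but the scale can be left at either end. A previous score of 6 with a ratio of 1.5 gives 9; a previous score of 1 with a ratio of 0.5 gives 0.5.

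**Size of one bad record.** An item of 20 instead of 6 changes that participant's ACQ-7 by 14/7 = 2.0, and the mean of 29 placebo participants by 2.0/29 = 0.07.

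**The case against.** The strongest reply is that this rarely matters. Neither document says how often exactly one item will be missing. Both a local and a central FEV1 reading exist, so item 7 may seldom be absent. ACQ-7 is not in the hierarchy of SAP 8.2.5, so no confirmatory claim depends on it. SAP 15.3 presents its handling as based on the ACQ manual, which cannot be checked here, and its worked example uses a symptom question. The points on frequency and consequence stand. The rest does not remove the defect: the heading names ACQ-7, the trigger is any one question, item 7 is counted among the seven, and 20 is not a valid value on a 0-6 item whatever the source.

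Three stronger readings are tempting and are not supported.

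- A reader might infer that ACQ-7 totals will often exceed 6. The enumeration shows that this is rare.
- A reader might infer a material bias between arms, because symptoms should improve more on dupilumab. A simulation of Day 1 to Week 4 with assumed item distributions made the filled item 7 too favourable by about 1.1 points (dupilumab-like change) and 0.8 (placebo-like), or (1.1 − 0.8)/7 = 0.04 ACQ-7 points per affected record. If 5% of records were affected (assumed), the shift is 0.04 × 0.05 = 0.002.
- A reader might infer that an FEV1 value between two bands of Table 5 counts as missing and triggers the rule. The bands are in whole percentages, rounding is the ordinary reading, and a measured value is not a missing answer.

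**Conclusion.** The rule in SAP 15.3, applied as written, gives wrong or undefined results in identifiable cases. This is a defect in a stated rule, not merely missing detail. The filled item can leave its scale, sometimes by a wide margin; the ratio is undefined after an all-zero post-baseline visit; and a missing FEV1 band is derived from symptoms and reliever use. The arithmetic rests only on the documents. How often it would happen rests on an unstated rate of single missing items. The effect on arm means is probably small and no type I error claim is affected. It is a minor point, worth correcting because the correction is cheap and avoids unplanned decisions at analysis.

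**What to change.** In SAP 15.3:

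1. Cap the filled item at 0 to 6 (1 to 7 for AQLQ(S)). The largest possible ACQ-7 is then (36 + 6)/7 = 6.
2. If the previous-visit sum is 0, use the fallback already in the SAP, the mean of the items completed at the current visit.
3. Apply the ratio only to items 1 to 6, with items 1 to 6 in both sums.
4. For item 7, use the locally read FEV1 if the central value is missing. If neither exists, leave ACQ-7 missing for the MMRM and still report ACQ-5 and ACQ-6.

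If the ACQ manual prescribes something different, record the departure and the reason. The cost is a short paragraph of SAP text and a few lines of derivation code. The downside is that a few ACQ-7 scores become missing instead of filled.
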